6.5 CONCOMITANT THERAPY

Participants may use concomitant pharmacologic treatments for pelvic pain during this study, provided that they remain on stable dosages of these medications. This includes using stable dosages of prescribed or over-the-counter analgesics. However, participants will be instructed to avoid initiating, dose-escalating, dose de-escalating, or weaning off of analgesic medications during the study. Further, participants will be asked to avoid initiating, dose-escalating, dose de-escalating, or weaning off medications that may affect their mood, such as antidepressants or anxiolytics.

Participants may engage in other forms of informal aerobic exercise such as jogging, swimming, or hiking. However, they will be instructed to avoid engaging in outside organized yoga or physical conditioning activities during the study, such as attending outside yoga or physical conditioning classes or workshops. Participants will also be asked to avoid using formal psychological therapies (e.g., systematic desensitization, sex therapy, cognitive therapy, relaxation therapy), mindfulness (e.g., formal meditation or mindfulness training sessions) or behavioral therapies (e.g., pelvic floor rehabilitation or biofeedback performed by certified healthcare practitioners) directed at pelvic pain during the study, although they may engage in psychological or behavioral interventions directed at other physical or mental health problems.

Participants will also be asked to avoid undergoing invasive procedures for their pelvic pain during the study. This includes surgical resection or invasive treatment of endometriosis, pelvic scar tissue, vulvar/vestibular tissue, or uterine myomas or polyps as potential contributors to chronic pelvic pain.

The recommendation to avoid using concomitant therapies will apply to both the main 8-week intervention phase of the study and the post-intervention follow-up period. However, only the former will constitute a protocol deviation; use of the above concomitant therapies during the post-intervention follow-up period will not be classified as a protocol deviation (see section 10.1.10, Protocol Deviations).

7 STUDY INTERVENTION DISCONTINUATION AND PARTICIPANT WITHDRAWAL

7.1 DISCONTINUATION OF STUDY INTERVENTIONS

Participants may discontinue participation in study interventions at any time, although the investigative team will strive to minimize early discontinuation except when necessary for participant safety. Investigators may also discontinue a participant's involvement in study interventions for the following reasons:

- Continued participation would not be in the best interest of the participant or might require an additional treatment that would confound interpretation of the study data
- Disruptive behavior by a study participant that interferes with the conduct of study intervention classes
- New development or discovery of a study exclusion criterion that precludes further study participation

When a participant discontinues her participation in study yoga or physical conditioning classes or home practice but does not withdraw from the overall study, attempts will be made to complete remaining study procedures as indicated by the study protocol. At the time of intervention discontinuation, the study team will document:

- The reason(s) for discontinuing participation in study interventions,
- Whether the participant is expected to continue study follow-up assessments

If the reasons for discontinuation of study interventions is an Adverse Event (AE) or Serious Adverse Event (SAE), or unanticipated problem, study staff will collect information about the AE/SAE or unanticipated problem and document that this is the cause of study intervention participation (see sections 8.3 and 8.4).

7.2 PARTICIPANT WITHDRAWAL FROM THE STUDY

Participants may also withdraw from participation in the overall study at any time upon request, although the investigative team will strive to minimize participant withdrawal from the overall study except for safety reasons. The study investigators may also discontinue a participant's involvement in the study for the following reasons:

- Lost-to-follow up, or inability to contact the participant (see **Section 7.3, Lost to Follow-Up**)
- Occurrence of any event or medical condition or situation that indicates that continued collection of follow-up study data would not be in the best interest of the participant or would confound interpretation of the study data
- Disruptive behavior by a study participant that interferes with the conduct of future study visits
- New development or discovery of a study exclusion criterion that precludes further study participation

The reason for participant discontinuation or withdrawal from the study will be recorded on study forms at the time of early discontinuation. Participants who sign the informed consent form and are randomized but do not receive the study intervention may be replaced by other participants if these are identified early enough to allow their participation in study intervention programs. Participants who sign the informed consent form, and are randomized and receive the study intervention, and subsequently withdraw or are discontinued from the study will not be replaced.

If the reason for a participant's withdrawal from the study is an Adverse Event (AE), Serious Adverse Event (SAE), or unanticipated problem, study staff will collect information about the AE/SAE or unanticipated problem and document that this is the cause of participant withdrawal (see sections 8.3 and 8.4).

7.3 LOST TO FOLLOW-UP

An enrolled participant will be considered lost to follow-up if she misses two consecutive study visits after randomization and is unresponsive to study contact or is no longer participating in study activities. The following actions will be taken if a participant misses a required study visit:

- The site will attempt to contact the participant, reschedule the missed visit (within recommended time windows if possible), counsel the participant on the importance of maintaining the assigned visit schedule and ascertain if the participant wishes to and/or should continue in the study
- Before a participant is deemed lost to follow-up, the investigator or designee will make every effort to regain contact with the participant (where possible, 3 telephone calls and/or e-mail messages). These contact attempts will be documented in the participant's medical record or study file.
- If the participant continues to be unreachable, she will be considered to have withdrawn from the study with a primary reason of lost to follow-up.

8 STUDY ASSESSMENTS AND PROCEDURES

8.1 NON-SAFETY ASSESSMENTS

This trial involves the following procedures required for: 1) Screening/Baseline Evaluations; 2) Randomization and Blinding, 3) Therapeutic Interventions, and 4) Follow-Up Evaluations below:

1. SCREENING/BASELINE EVALUATIONS

Preliminary eligibility will be determined by research coordinators through a Screening Telephone Interview followed by a video-based Screening Visit. The final review of eligibility will take place after a clinic-based Baseline Visit, after which candidates will be eligible for randomization.

All screening evaluations will be conducted by clinical coordinators affiliated with UCSF or Stanford University. Clinic visits will take place in outpatient facilities of UCSF in the city of San Francisco, rented research facilities in Oakland, CA affiliated with UCSF, or outpatient facilities of Stanford University. All screening procedures must be completed within a 2-month period; if screening cannot be completed within this period, initial procedures will be repeated to ensure that eligibility has not changed before randomization.

Telephone Screening Interview

- Women who call in response to recruitment advertisements will be provided with a brief overview of the study goals and procedures by a clinical coordinator over the telephone.
- If interested, candidates will complete a brief telephone survey to assess preliminary eligibility (including age, gender, duration/severity of pelvic pain, current and past pelvic pain treatment, prior yoga or stretching/strengthening practice, exclusionary conditions and medications, and availability for upcoming group intervention classes).

Screening (Video) Visit

- Before or at this visit, a coordinator will explain the requirements of the study while referring to an IRB approved informed consent form, and candidates will provide informed consent if they are interested in proceeding with the study.
- Candidates will complete questionnaires about their demographic, medical, pain-related, and urologic/gynecologic history for eligibility assessment.
- Over-the-counter and prescription medications will be reviewed to assess for recent initiation, escalation, or weaning of medications that would be exclusionary.
- Candidates will provide information about their recent use of computers and mobile electronic devices and confirm their access to devices and the internet.
- Potentially eligible women will provide information about their overall physical function and history of physical activity.

- Potentially eligible women will be instructed on completing 7-day diaries to document baseline pain severity and sexual activity before the Baseline Visit.
- Potentially eligible women will also be asked to complete questionnaires about substance use, trauma history, pain-related functioning, sexual functioning, anxiety and depression symptoms, sleep quality, and pain cognitions/self-efficacy and return them by the Baseline Visit.

Baseline Clinic Visit

- Candidates will return with their completed 7-day diaries and questionnaires, and results will be reviewed by a clinical coordinator for eligibility (particularly regarding the pain logs).
- A clean catch urine sample will be collected to assess for possible urinary tract infection or hematuria and rule out pregnancy (for women of reproductive potential).
- Height and weight measurements will also be obtained for characterization of the study sample.
- Physical performance, including balance testing, lower extremity strength, and aerobic endurance will be assessed by a coordinator.
- Participants will be invited to undergo optional pelvic floor tenderness evaluations by a clinician investigator or consultant experienced in gynecologic evaluation.
- If the Baseline Clinic Visit takes place within 2 weeks of the start of the next intervention orientation session, eligible participants will be randomized to one of the two interventions at this visit (see below).

3. FOLLOW-UP EVALUATIONS

Follow-up evaluations after the start of the study intervention programs will consist of a 2-week telephone call, 4-week video visit, 6-week telephone call, 8-week video visit, and 8-week post-intervention video visit:

2-Week Telephone Call

- Two weeks after the start of the intervention programs, coordinators will call women to assess adverse events, address any concerns, and reinforce adherence to group classes and home practice of yoga or stretching/strengthening exercises.

4-Week (Video) Visit

- Four weeks after the start of the intervention programs, women will have a follow-up video visit, by which time they will be asked to complete follow-up pain diaries for data abstraction by blinded analysts.
- Adverse events will be assessed using standardized procedures and forms.

- Home practice logs will be reviewed, and yoga/stretching self-efficacy questionnaire measures will be re-administered.
- Women will re-self-administer questionnaires about pain-related outcomes including pain-related functioning, sexual functioning, anxiety and depression symptoms, sleep, and pain-related cognitions/self-efficacy.
- Women will undergo repeat assessment of physical performance.
- Current use of prescription and over-the-counter medications and use of co-interventions will be re-reviewed and recorded.

6-Week Telephone Call

- Six weeks after the start of the intervention programs, coordinators will call women to assess adverse events, address any concerns, and reinforce adherence to group classes and home practice of yoga or stretching/strengthening exercises.

8-Week (Video) Visit

- Eight weeks after the start of the intervention programs, women will return for another video visit, bringing their third set of pain diaries for data abstraction by blinded analysts.
- Adverse events will be assessed using standardized procedures and forms.
- Home practice logs will be reviewed, and yoga/stretching self-efficacy questionnaire measures will be re-administered.
- Women will return self-administered questionnaires about pain-related outcomes that they completed for the 4-week visit.
- Women will undergo repeat assessment of physical performance.
- Current use of prescription and over-the-counter medications and use of co-interventions will be re-reviewed and recorded.
- Women will be encouraged to continue practicing yoga or stretching/strengthening exercises for at least two hours per week and record this practice in their home practice logs.

8 Week Post-Intervention (Video) Visit

- Eight weeks after completion of the intervention programs, participants will return for another video visit, returning their fourth set of pain diaries for data abstraction by a blinded analyst.
- Adverse events will be reassessed using standardized procedures and forms.
- Home practice logs will be collected and reviewed, and yoga/stretching self-efficacy questionnaire measures will be re-administered.

- Women will return the same self-administered questionnaires about pain-related outcomes as they completed for the 8-week visit.
- Current use of prescription and over-the-counter medications and use of co-interventions will be re-reviewed and recorded.
- A closeout satisfaction questionnaire will be administered that includes assessment of satisfaction with and barriers to intervention practice.

8.2 RISK/BENEFIT ASSESSMENT

8.2.1 KNOWN POTENTIAL RISKS

Study interventions and procedures may pose the following risks to participants:

- a) **Yoga Intervention**: Possible risks associated with group yoga instruction and home yoga practice include muscle soreness and muscle/ligament strain, or other musculoskeletal injury sustained by participants while trying to practice yoga poses.
- b) **Stretching/Strengthening Control Intervention**: Similar to the yoga intervention, possible risks associated with the stretching/strengthening control intervention include muscle soreness and muscle/ligament strain, or musculoskeletal injury sustained by participants while trying to learn or practice the stretching exercises.
- c) **Questionnaires and Diaries**: Although the information participants provide on data collection forms and diaries is confidential, some participants may feel embarrassed at having to answer questions, especially those related to sexual function, anxiety, or depression. There will be slight inconvenience in time and effort to complete diaries and questionnaires.
- d) **Physical Exam Measurements**: There are no direct risks associated with undergoing measurement of height and weight, although participants may experience this as inconvenient or unpleasant.
- e) **Pelvic Floor Assessment**: Digital pelvic examination and assessment of pelvic floor muscle tenderness and hypertonicity may be associated with discomfort or soreness in the perineal or vaginal area, emotional reaction to being touched in the genital area, feeling of fullness or pressure in the rectum, or urge to urinate during or following the exam.
- f) **Urinalysis and Urine Pregnancy Testing**: There are no direct risks associated with collection of the clean-catch urine sample, although some participants may experience this as inconvenient or unpleasant.

8.2.2 KNOWN POTENTIAL BENEFITS

Potential benefits of the yoga program: Participants in the yoga intervention group will receive free instruction in alignment-based yoga techniques through the 8-week yoga program, as well as a limited set of yoga props that they can use to practice study yoga techniques at home. Regardless of the yoga intervention's effects on their pelvic pain or pain-related functioning, participants may find that regular practice of these yoga

techniques is associated with improvement in their general health and well-being. Prior studies of Hatha yoga interventions have reported that participants experience improvement in anxiety or depression symptoms, sleep quality, physical function, and/or overall quality of life, although those studies may have focused on different populations or involved alternate yoga techniques.

Potential benefits of the stretching/strengthening program: Participants in the physical conditioning intervention group will receive free instruction in performing general muscle stretching/strengthening exercises through the 8-week yoga program, as well as a limited set of props that they can use to practice exercises at home. Regardless of the control intervention's effects on their pelvic pain or pain-related functioning, participants may find that regular practice of these exercises is associated with improvement in their general health and well-being. Prior studies of physical conditioning programs have reported that participants experience improvement in anxiety or depression symptoms, sleep quality, physical function, and/or overall quality of life, although those studies may have focused on different populations or involved alternate physical conditioning techniques.

Potential benefits of discussing pelvic pain in a study context: Indirectly, participants in both intervention groups may find it comforting to discuss their pelvic pain, associated anxiety or depression symptoms, and other pelvic symptoms with study personnel, intervention instructors, or other participants in their intervention classes. They may feel empowered by their participation in a group intervention program that acknowledges the impact of pelvic pain on their day-to-day lives. They may benefit from informally sharing their strategies for coping with their pain with other afflicted women.

Potential benefits of other study measurements: Study measurements performed as a part of this study may also reveal incidental abnormalities in participants' blood pressure, heart rate, or mood that will be shared with participants. This may prompt participants to seek further evaluation or treatment through their regular source of health care, which may in turn lead to improvements in their health.

8.2.3 ASSESSMENT OF POTENTIAL RISKS AND BENEFITS

Although participation in this study is associated with risks, these risks can be minimized through the following protective measures:

Yoga Intervention: The instructors leading the group yoga classes will be trained yoga teachers who have experience in teaching adults from a wide range of ages to learn and practice yoga safely, and who will undergo specific, in-person training by the study's yoga expert consultants. The study intervention protocol is designed to avoid precipitating pelvic floor strain and incorporates yoga props such as blocks and blankets to help participants perform yoga postures in such a way that will minimize the likelihood of muscle strain or musculoskeletal injury. The yoga instruction manuals are designed to include explicit tips on modifying or adapting postures to accommodate problems with mobility, flexibility, or balance.

Stretching/Strengthening Intervention: Instruction for the control intervention classes will be provided by trained physical therapists or personal trainers who are experienced in teaching patients of all ages to perform physical exercises safely, and who have completed in-person training with the study expert physical therapy consultant. Stretching and strengthening exercises have been selected to be appropriate for women who may have flexibility or mobility limitations in addition to pelvic pain.

Questionnaires and Diaries: Any paper-based questionnaires or diaries collected in this research will be stored in a locked file cabinet in a locked room in research facilities, and data obtained from diaries and questionnaires will be stored on password-secured servers. All study staff will be fully trained in good clinical practice and HIPAA procedures, and the importance of participant confidentiality will be emphasized.

Physical Examination Measures: Study coordinators who are responsible for obtaining general physical exam measures will have prior experience with performing physical exam measurements in women of all ages (through the investigators' other clinical studies), and/or will receive study-specific training to ensure that they perform measurements in a manner that is sensitive and minimizes discomfort to participants.

Pelvic Floor Assessment: Assessment of pelvic floor tenderness and hypertonicity will be performed by investigators experienced with performing gynecologic and pelvic exams (e.g., [name], [name], [name]) with experience performing pelvic exams for clinical care in a manner that is sensitive and minimizes discomfort to participants. Even if they agree to undergo this assessment, participants will be informed that they can ask to stop the exam for any reason. Women with a history of pelvic/sexual trauma or extreme pain with the pelvic exam can decline this measurement but still take part in other study procedures.

Urinalysis and Pregnancy Testing: Study coordinators who are responsible for performing urine testing will be trained to instruct participants on providing urine samples in a manner that is sensitive and minimizes embarrassment.

Because the potential risks to participants are modest and can be managed through the above protective measures, the study team believes the benefits of the knowledge to be gained from the study, as well as the indirect potential benefits to women from study participation, outweigh the potential risks.

8.3 SAFETY ASSESSMENTS

Clinical coordinators will proactively monitor participant safety by asking participants about negative changes in health at scheduled follow-up visits and telephone calls starting with the 2-Week Telephone Call. Negative changes in health reported by participants will be recorded as adverse events on standardized forms as appropriate.

Coordinators will not prompt participants to provide information about specific types of adverse events, but instead will encourage participants to volunteer information by asking the standardized, open-ended question, "Have there been any changes in your health since your last visit?" Any negative changes in health reported in response to this question will then be recorded on standardized forms.

Participants will also be given telephone numbers at the Screening Clinic Visit to call study staff before the scheduled 2-week telephone call or between scheduled study visits or calls to report negative changes in their health. If reported, these changes will be recorded on standardized adverse event forms.

8.4 ADVERSE EVENTS AND SERIOUS ADVERSE EVENTS

8.4.1 DEFINITION OF ADVERSE EVENTS

For this study, an adverse event (AE) is defined as any untoward or unfavorable medical occurrence in a study participant, including any abnormal sign (e.g. abnormal physical exam or laboratory finding), symptom, or disease, temporally associated with the participants' involvement in the research, whether or not considered related to participation in the research. In general, medical conditions or diseases present before starting study interventions should only be considered adverse events if they worsen after starting the interventions.

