8.4.3.2 RELATIONSHIP TO STUDY INTERVENTION

All AEs will also be categorized according to the likelihood that they are related to the therapeutic study interventions. Specifically, AEs will be labeled as unrelated, unlikely related, possibly related, probably related, or definitely related, based on the opinion of the Site PI:

- *Unrelated*: the time course between administration of the study intervention and occurrence or worsening of the AE rules out a causal relationship, and/or another cause is confirmed and no indication of involvement of the study intervention in the occurrence or worsening of the AE exists.
- *Unlikely related*: the time course between administration of the study intervention and occurrence or worsening of the AE makes a causal relationship unlikely, and/or; the known effects of the study intervention provide no indication of involvement in the AE and another cause adequately explaining the AE is known, and/or; a plausible causal chain may be deduced from the known effects of the study intervention, but another cause is much more probable, and/or; another cause is confirmed and involvement of the study intervention in the AE is unlikely.
- *Possibly related*: a plausible causal chain may be deduced from the nature of the study intervention, but another cause just as likely to be involved is also known, or; although the nature of the intervention does not create a strong expectation of involvement in the AE, involvement of the intervention is still possible, and no other cause gives adequate explanation.
- *Probably related*: The nature of intervention indicates that it probably caused the AE, and/or; the course of the AE after stopping study intervention improved and, if applicable, worsened after re-challenge, and/or; a specific test suggests the involvement of the study intervention, although another cause cannot be ruled out.
- *Definitely related*: The biological properties of the study intervention are known to cause the AE, and/or; the AE improves after stopping study intervention and, if applicable, worsens after re-challenge, and/or; a specific test indicates the involvement of the study intervention, and no indication of other causes exists.

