8.4.4 TIME PERIOD AND FREQUENCY FOR EVENT ASSESSMENT AND FOLLOW-UP

New AEs or SAEs will be considered reportable any time after the Baseline Clinic Visit (which is the first scheduled visit involving in-person assessments) until 7 days (for non-serious AEs) or 30 days (for SAEs) after the last day of study participation.

Clinical coordinators at each site will proactively assess for adverse events by asking participants about negative changes they have experienced in their health at scheduled follow-up study visits and telephone assessments starting with the 2-Week Telephone Call. Coordinators will not prompt participants to provide information about specific types of adverse events, but instead will encourage participants to volunteer information by asking a standardized, open-ended question, “Have there been any changes in your health since your last visit?” Any negative changes in health reported in response to this question will then be recorded on standardized forms.

Participants will also be given telephone numbers at baseline to call study staff before the scheduled 2-week telephone call or between scheduled study visits or calls to report negative changes in their health. If reported, these changes will be recorded on standardized adverse event forms.

Medical or psychiatric conditions that are present at the time that participants are screened will be considered to reflect participants' baseline status and will not be reported as adverse events. However, if the study participant's condition deteriorates at any time during the study, this deterioration will be recorded as an AE even if it is related to a pre-existing condition.

Adverse events will be characterized by clinical coordinators at each clinical site in collaboration with the Site Principal Investigator (Site PI) or other investigators if appropriate. The clinical coordinator in conjunction with the Site PI will document events on standardized adverse event forms. The Site PI will review information about individual AEs collected by clinical coordinators twice monthly to guide determinations about the relationship to study interventions, expectedness, and severity.

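### Capture of harms from the baseline pelvic floor examination is passive and inconsistently defined: 8.4.1 and 8.4.4 use different start points, no one asks before the 2-week call, and relatedness to study procedures is not rated

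*Combined protocol and SAP*

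**What the plan says.** **The procedure and its harms.** Section 8.2.1(e) says that the digital pelvic examination "may be associated with discomfort or soreness in the perineal or vaginal area, emotional reaction to being touched in the genital area". It also lists a feeling of rectal fullness or pressure "or urge to urinate during or following the exam". Section 8.1 places the examination under the Baseline Clinic Visit, before randomization: "Participants will be invited to undergo optional pelvic floor tenderness evaluations by a clinician investigator or consultant experienced in gynecologic evaluation". A footnote to the Schedule of Activities (1.3) allows it at a different time by agreement.

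**The AE rules.**

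- Section 8.4.1 first defines an AE broadly, as any unfavorable sign, symptom or disease linked in time to taking part in the research, whatever its cause. It then adds, qualified as a general rule, that "medical conditions or diseases present before starting study interventions should only be considered adverse events if they worsen after starting the interventions".
- Section 8.4.4 sets the reporting window: "New AEs or SAEs will be considered reportable any time after the Baseline Clinic Visit". It notes that this is the first scheduled face-to-face visit. It also says that "conditions that are present at the time that participants are screened will be considered to reflect participants' baseline status", and that a participant's deterioration is an AE whenever in the study it happens.
- Section 8.4.3.2 requires AEs to be "categorized according to the likelihood that they are related to the therapeutic study interventions".
- Section 8.3 has coordinators ask about health changes "at scheduled follow-up visits and telephone calls starting with the 2-Week Telephone Call". Participants also receive telephone numbers for reporting problems before that call, and reported problems go on AE forms.
- The AE row of the Schedule of Activities has no mark at the Baseline Visit.

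**The concern.** The pelvic examination is the most intrusive assessment in the trial, and the protocol itself names its harms. It takes place before the interventions, and the AE rules are written mainly around the interventions. Two coordinators, each following a different section correctly, could classify the same event between the Baseline Visit and the first class differently. A harm that begins and ends within the visit may not be counted at all. A recorded event can be rated only for its relation to yoga or physical conditioning, so nothing on the scale shows that a study procedure caused it.

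Section 4.2 says that the pilot includes nearly all the procedures envisaged for the full-scale trial. If the examination is carried forward, a low count of examination harms collected under these rules would be weak evidence that it is well tolerated.

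**Working it through.** No sample size, power or event figure bears on this point. The check sets the rules side by side and then works out the delay before the first scheduled enquiry.

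**Step 1. Classify four events under each section.**

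| Event | 8.4.4 | Second sentence of 8.4.1 | Scheduled enquiry |
|---|---|---|---|
| A. Harm begins and ends during an examination at the Baseline Visit | Outside the window, read literally | Precedes the interventions; can be read to exclude it | None at the visit; the 2-week question asks about changes since the previous visit, so does not naturally reach events during it |
| B. New soreness the day after the Baseline Visit, before the interventions | Inside the window | Can be read to exclude it unless it later worsens | 2-week call |
| C. Harm during an examination held on a later day, before the interventions | Inside the window | Same ambiguity as B | 2-week call |
| D. Pain present at screening worsens after the examination, before the interventions | Deterioration, so an AE | In general not an AE, because the worsening came before the interventions | 2-week call |

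Event D is the clearest conflict. The two sections give opposite answers about the same worsening, in a population enrolled because it already has pelvic pain.

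**Step 2. Attribute the event.** Under 8.4.3.2, an event that precedes the intervention falls in the unrelated category, because the time course rules the intervention out. That rating is correct as far as it goes. The scale has no field in which to record a relation to the examination.

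**Step 3. Delay to the first scheduled enquiry.**

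- Inputs: randomization takes place at the Baseline Visit if that visit is within 2 weeks of orientation (8.1, Baseline Clinic Visit), so the gap is 0 to 2 weeks. The first call is 2 weeks after the programs start (8.1, Follow-Up Evaluations).
- Assumptions: the programs start at orientation, and the examination is done at the Baseline Visit.
- Formula: delay = (Baseline Visit to program start) + 2 weeks.
- Shortest: 0 + 2 = 2 weeks. Longest for women randomized at that visit: 2 + 2 = 4 weeks.
- If the Baseline Visit is more than 2 weeks before orientation, the delay exceeds 4 weeks. The documents schedule no AE contact in that interval.

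**Step 4. Women examined but not randomized.** They receive no follow-up calls or visits, so no AE enquiry is scheduled for them. To bound the number, take the 9.4.2 benchmark of randomizing at least 50% of women with screening visits. At exactly 50%, 36 randomized women imply 36 / 0.50 = 72 screened, and 72 − 36 = 36 not randomized. The documents do not say how many of these would reach the Baseline Visit or accept the examination, so at that benchmark the range is 0 to 36. This is a bound, not an estimate.

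**The case against.** A reader might infer that examination harms cannot be captured at all, or that 8.4.1 removes every one of them. The documents do not support either reading:

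- The first sentence of 8.4.1 covers new symptoms whatever their cause.
- Soreness or urgency that begins after the visit is inside the 8.4.4 window, can be telephoned in and put on an AE form, and is within the look-back of the 2-week question.
- If the examination is held on a day after the Baseline Visit, even harms during it are inside the window.
- The restriction in 8.4.1 is a general rule about existing conditions or diseases. Applying it to a new symptom caused by a study procedure is one reading, not the only one.
- Relatedness affects how an event is classified, not whether it is recorded. Section 8.4.5 lets the principal investigator consult the IRB on non-serious events linked to procedures, and 8.4.6 still has unrelated serious events reported.
- Section 8.5.1 covers research-related problems that are unexpected in nature, severity or frequency, so a listed harm that proves worse or more common than described can still qualify.

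The examination is also optional, done by experienced clinicians and stoppable on request (8.2.3), and its tolerability is not one of the feasibility benchmarks.

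All of this stands, and it limits the point. It does not remove the conflict between 8.4.1 and 8.4.4, the gap for harms confined to the visit, or the missing procedure category. The telephone route depends on the woman choosing to call, and the sections disagree on when she gets the numbers: 8.3 says at a screening clinic visit, although the Screening Visit is by video, and 8.4.4 says at baseline. Consulting the IRB under 8.4.5 is optional and concerns reporting, not collection. Harms of the kind and degree listed in 8.2.1(e) would not count as unexpected under 8.5.1.

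**Conclusion.** The defect is real and moderate in size. Post-visit harms can be recorded if the woman volunteers them, but the rules have four weaknesses:

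1. Read literally, they leave out harms confined to the Baseline Visit.
2. They give conflicting answers for events between that visit and the start of the interventions.
3. They schedule no enquiry until about 2 to 4 weeks after the examination for women randomized at the Baseline Visit, later if that visit is earlier, and none for women examined but not randomized.
4. They offer no way to rate relatedness to a study procedure.

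The 2-to-4-week figure assumes that the programs start at orientation and that the examination is done at the Baseline Visit. A reader might go further and predict that the pilot will show few or no examination harms because of its collection rules. The documents give no harm rate or uptake figure from which to judge that. What they support is that a low count could not be taken as good evidence of tolerability.

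**What to change.** 1. Reconcile 8.4.1 and 8.4.4 on one start point: the first in-person study procedure at the Baseline Clinic Visit. Use it both for the opening of the reporting window and for deciding what counts as pre-existing. If the footnote to the Schedule of Activities is meant to allow an examination before that visit, the start point should cover it too.
2. Mark the AE row of the Schedule of Activities at the Baseline Visit. Ask the existing open-ended question at the end of that visit and after any separately scheduled pelvic examination, including for women not then randomized. Word its look-back to include the visit itself.
3. Add a field to the AE form for relatedness to study procedures, beside the existing rating for the interventions.
4. Tabulate pre-intervention events separately, so that the by-arm tables hold only events after the interventions start.
5. Align 8.3 and 8.4.4 on when the telephone numbers are given out.

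The cost is protocol wording, one mark in the schedule, one form field and one question, asked at an existing contact. The downside is a few more AE forms and a slightly higher total AE count.
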